## **1) Deaths**

All deaths:

- while the subject is receiving treatment on a protocol
- up to 60 days (autologous) or 90 days (allogeneic) after last dose of protocol treatment
- or any death that occurs more than 60 days (autologous) or 90 days (allogeneic) after protocol treatment has ended that is felt to be treatment related.

Reports will include deaths from the common and expected Grade 4 toxicities noted below. Deaths that occur outside of Stanford will be reported whenever possible. It must be noted that obtaining detailed information on the cause and circumstances of a death occurring at another institution can be difficult. Excludes deaths related to relapse of underlying disease, which will be reported to the IRB at the time of protocol renewal.

## **2) All serious and unexpected toxicities**

Defined as those toxicities not identified in the transplant literature, product inserts, or study consent form.

The following will be *recorded*, but generally will **not** be *reported* as AEs or SAEs, unless also considered related to the study drug.

### **1) Hospitalizations**

Approximately 50% of allogeneic transplant recipients will be readmitted to the hospital. The most common indications for readmission of an allogeneic HCT recipient are fever, failure to maintain nutritional status, and GvHD. NOTE: Events that result in hospitalization or extend hospitalization will still be considered SAEs.

### **2) Relapse of disease**

Relapse unfortunately remains a significant problem following both autologous and allogeneic HCT. The risk of relapse is influenced by both subject and disease variables. The risk of relapse following allogeneic transplant is extremely dependent on the disease being treated but ranges from 10% (for subjects with severe aplastic anemia) to 80% (for subjects with refractory acute leukemia).

### **3) Common and expected toxicities of HCT $\leq$ Grade 4 that are well-described in transplant literature, the product inserts, or study consent form and do not result in death.**

In general, these toxicities are considered reversible. The specific reporting requirements are found in the protocol. These Grade 4 toxicities include, but are not limited to, alopecia, anemia, anorexia, bleeding requiring transfusions, cardiac arrhythmias, central venous catheter infections, constipation, diarrhea, edema, fatigue, febrile episodes, gastritis, graft failure, graft versus host disease, hematuria, hypertension, hypotension, hypoxia, incontinence, infections, insomnia, laboratory abnormalities, mental status changes, mood alterations, mucositis, nausea, neutropenia, pain, pleural effusion, pneumonitis, rash, seizures, sepsis, sinusoidal obstructive syndrome, tachycardia, thrombocytopenia, thrombotic microangiopathy, tremor, vomiting. For IND studies, SAEs that are SUSARs per 21CFR§312.32 will be reported as IND Safety Reports (see above).

### **4) Acute and chronic GvHD**

Acute and chronic GvHD are major complications of HCT and account for most non-relapse mortality. The incidence of GvHD will be reported as part of the secondary outcomes and to the IRB at the time of the protocol annual review.

## **5) Secondary Malignancies**

The occurrence of secondary malignancies and associated mortality is a known risk of cancer therapies. The occurrence of secondary malignancies will be reported to the IRB at the time of the protocol annual review.

## **6) Special reporting situations** which may require expedited reporting and/or safety evaluation include, but are not limited to:

- Overdose of any study drug
- Suspected abuse/misuse of a study drug
- Inadvertent or accidental exposure to a study drug
- Medication error involving a product (with or without subject exposure to the study drug)

Occurrence of any special reporting situation should be recorded in the CRF. If any special reporting situation meets the criteria for an adverse event, it should be recorded on the adverse events CRF. If the adverse event is considered serious, it should be recorded on the adverse events CRF as serious and should be reported on the Serious Adverse Event Report Form. The SAE Report Form should be sent via email or fax to Pharmacyclics Drug Safety or designee within 15 days of awareness.

## **Adverse Events of Special Interest (AESI)**

Specific adverse events, or groups of adverse events, will be followed as part of standard safety monitoring activities. The following events (regardless of seriousness) will be reported to Pharmacyclics Drug Safety per SAE reporting timelines.

### **Major Hemorrhage**

Major hemorrhage is defined as any of the following:

- Any treatment-emergent hemorrhagic adverse events of Grade 3 or higher\*. Any treatment-emergent serious adverse events of bleeding of any grade
- Any treatment-emergent central nervous system hemorrhage/hematoma of any grade

\*All hemorrhagic events requiring transfusion of red blood cells should be reported as Grade 3 or higher AE per CTCAE v4.0.

Events meeting the definition of major hemorrhage will be captured as an event of special interest.

## **Expediting Reporting Requirements for Serious Adverse Events**

All serious adverse events and AESIs (initial and follow-up information) will be reported on FDA Medwatch (Form 3500A) or Suspect Adverse Event Report (CIOMS Form 1) IRB Reporting Form and sent via email ([REDACTED] [@pcyc.com](mailto:@pcyc.com)) or [contact]) to Pharmacyclics Drug Safety, or designee, within 15 days of

the event. Pharmacyclics may request follow-up and other additional information from the Sponsor Investigator.

All serious adverse events that have not resolved by the end of the study, or that have not resolved upon discontinuation of the subject's participation in the study, must be followed until any of the following occurs:

- The event resolves
- The event stabilizes
- The event returns to baseline, if a baseline value/status is available
- The event can be attributed to agents other than the study drug or to factors unrelated to study conduct
- It becomes unlikely that any additional information can be obtained (subject or health care practitioner refusal to provide additional information, lost to follow up after demonstration of due diligence with follow-up efforts)

## **8. CORRELATIVE/SPECIAL STUDIES**

We propose a series of correlative laboratory studies using blood samples collected from study participants, with the aim of elucidating the impact of ibrutinib on immune reconstitution after allogeneic HCT and on the development of alloreactivity, graft--vs-tumor effects, and GvHD.

### **Background**

Alloreactive T- and B-cells play a crucial role in development of both beneficial graft-vs-tumor effects and harmful GvHD after allogeneic HCT. In chronic GvHD, T follicular helper cells (TFH), Th2, and Th17 T-cells activate B-cells and elicit fibrotic cascades underpinned by alloantibody production and collagen deposition. To understand the impact of ibrutinib on alloreactivity after allogeneic HCT, we will perform global B- and T-cell immune phenotype analysis using multiplexed CyTOF analysis, focused on quantifying Th2 subversion and cytotoxic T-cell preservation, T follicular cell composition, and T-cell functional activation. These laboratory assays will be correlated with clinical evidence of GvHD and GVL effects (quantified by measuring minimal residual disease via sequencing of T- and B-cell immune receptors with clonoSEQ technology (in subjects with ALL) and via multi-parameter flow cytometry (in subjects with AML).

T- and B-cell repertoire reconstitution will be monitored via immune receptor high-throughput sequencing (HTS) and H-Y alloreactive B-cell phenotyping. We will determine the effect of ibrutinib on serum immunoglobulin levels, cytokine quantification, protective anti-EBV and anti-tetanus immunity, and allogeneic H-Y antibody responses after allogeneic HCT.

Minor histocompatibility antigens expressed on the Y chromosome are called H-Y antigens and are frequently targeted by female donor lymphocytes when male subjects undergo sex-mismatched transplantation (F→M HCT). [name] lab has demonstrated that H-Y specific B-cells and antibodies are associated with chronic GvHD following F→M HCT. We hypothesize that ibrutinib will preferentially target and deplete

alloreactive B-cell. While H-Y antigen provides a model system to study antigen-specific alloimmunity, H-Y can only be studied in male subjects with female donors (F→M HCT). Recognizing this limitation for H-Y antigen studies, as well as limitations in the number of PBMC available for research per subject, we have decided to dedicate F→M HCT subject samples to H-Y B-cell analyses while using samples from all other donor and recipient sex combinations (not F→M) for T-helper cell and functional T-cell analyses as shown in Table 3 below. Historically, F→M allotransplants account for 35-40% of cases of chronic GvHD.

### Sample collection

As in the PCYC 1129 protocol, 50 mL of blood will be collected in five 10 mL heparinized green-top tubes before the start of conditioning therapy; before ibrutinib initiation; and then again at Day +180, 1 year, and 1.5 years after allogeneic HCT. We will also obtain blood samples from the HCT donor. The 50 mL aliquots of recipient blood will be processed on-site at Stanford University, providing three vials of 1.5 mL plasma and five 1 mL vials of viably frozen peripheral blood mononuclear cells (PBMC) separated by Ficoll gradient centrifugation as described in the PCYC1129 laboratory manual. PBMC cell yields will be recorded and evenly distributed into five vials irrespective of cell quantity. Plasma will be stored at -80° C and PBMC will be stored in liquid nitrogen on-site. Comprehensive multiplexed B- and T-cell phenotype analysis will be performed on all samples at all time points using CyTOF. In addition, B- and T-cell repertoire analyses will be determined using immune receptor high-throughput sequencing (HTS). We plan to reserve a single vial of PBMC and 1 mL plasma per subject in central storage, in case trial investigators identify additional informative studies later.

[figure not shown]
**Table 3. Schedule of correlative laboratory studies.**

		Pre-HCT	Pre-Ibrut.	6 m	12 m	18 m
CyTOF B- and T-cell phenotyping (PBMC 1)	Res.	All	All	All	All	All
T-cell repertoire analysis by immune receptor sequencing (PBMC 2)	Res.	All	All	All	All	All
B-cell repertoire analysis by immune receptor sequencing (PBMC 2)	ALL SOC AML Res					All
IgG & IgM quantification	SOC	All	All	All	All	All
Cytokine Analysis and BAFF (plasma 1)	Res.	All	---	---	All	All
T-Follicular quantification (PBMC 3)	Res.	All but F→M				
H-Y alloreactive Antibodies (Plasma 2)	Res.	F→M only				
H-Y specific B-cell characterization (PBMC 4)	Res.	F→M only				

Abbreviations: HCT, hematopoietic cell transplantation; Ibrut, ibrutinib; m, months; Res, research; SOC, standard of care; AML, acute myeloid leukemia; ALL, acute lymphoblastic leukemia; F->M, female-donor-to-male-recipient; PBMC, peripheral blood mononuclear cells

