EXCLUSION CRITERIA	
 
Active involvement of the central nervous system with malignancy (previous CNS involvement is allowed if clearance of CNS disease has been documented prior to enrollment)
 
Pregnant or breastfeeding
 
Karnofsky Performance Status < 60%
 
Active leukemia (> 5% leukemic blasts in peripheral blood or bone marrow)
 
Non-hematologic malignancy with a life expectancy of < 5 years
 
Known history of human immunodeficiency virus (HIV) or active hepatitis C virus (HCV) or hepatitis B virus (HBV) infection. Subjects who are positive for hepatitis B core antibody or hepatitis B surface antigen must have a negative polymerase chain reaction (PCR) result before enrollment. Those who are PCR-positive will be excluded.
 
Known bleeding disorders (eg, von Willebrand's disease) or hemophilia.
 
History of other malignancies, except: 
 
Malignancy treated with curative intent and with no known active disease present for <math>\geq</math> 3 years before the first dose of study drug and felt to be at low risk for recurrence by treating physician.
 
Adequately treated non-melanoma skin cancer or lentigo maligna without evidence of disease.
 
Adequately treated carcinoma in situ without evidence of disease.
 
 
 

TREATMENT SUMMARY	Subjects will be treated with ibrutinib 420 mg orally once daily, starting between Day +60 and Day +90 after allogeneic HCT and continuing until 18 months post-transplant
SAMPLE SIZE	50 subjects enrolled and treated
STATISTICAL CONSIDERATIONS	Screening and enrollment of 50 subjects will provide 84% power to detect a decrease in the incidence of relapse at 18 months post-transplant from 45% to 25%

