- **In subjects with AML, myeloid blast crisis, or biphenotypic leukemia:** bone marrow examination, including assessment of minimal residual disease by multiparameter flow cytometry, at Day +90; Day +180; and 1 year post-transplant (**standard of care**). Please note: Okay to omit Day +90 MRD testing and Day +90 biopsy if previous biopsy (between Day +28 and Day +60) showed no evidence of disease.
- **In subjects with ALL or lymphoid blast crisis:** minimal residual disease testing by peripheral-blood high-throughput sequencing (ClonoSEQ) at Day +90; Day +180; 1 year; 1.5 years; and 2 years post-transplant (**standard of care**)
- Peripheral blood draw for mixed lymphocyte reactions, Th1/Th2 assays, and other correlative science at Day +90; Day +180; 1 year; 1.5 years; and 2 years post-transplant (**research**)

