## Correlative science aims

1. Perform immunophenotyping of peripheral-blood B- and T-cells before and after initiation of maintenance ibrutinib.
  - a. Evaluate Th1 polarization, effect on T follicular cells, and  $CD8^+$  cytotoxic T lymphocytes
  - b. Evaluate B-cell reconstitution by quantifying transitional, naïve, memory, and activated plasmablast fractions

- c. Determine concentrations of Th1 and Th2 cytokines in plasma
- 2. Characterize the B- and T-cell repertoire during and after ibrutinib maintenance using immune receptor high-throughput sequencing to assess clonal expansion of donor cytotoxic T-cells and follicular T-cells.
  - a. Compare to results from patients transplanted at our institution without maintenance ibrutinib
  - b. Quantify EBV-specific T-cell reconstitution
- 3. Assess B-cell function before and after initiation of maintenance ibrutinib
  - a. Evaluate for presence of alloreactive B-cells and H-Y antibodies in F->M allogeneic HCT
  - b. Quantify total serum immunoglobulin levels
  - c. Quantify protective anti-EBV and anti-tetanus antibodies
  - d. Assess levels of BAFF before, during, and after ibrutinib maintenance treatment

These laboratory studies will be correlated with clinical data (including onset, severity, and response of chronic GvHD and minimal residual disease detection of leukemia).

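### Table 3 leaves the pre-ibrutinib time point out of the cytokine/BAFF assay, so the only baseline precedes the transplant; whether any scheduled sample is off drug depends on an unreconciled treatment duration

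*Combined protocol and SAP*

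**What the plan says.** **Aims (Section 8, Correlative science aims).** Aim 3d is to "Assess levels of BAFF before, during, and after ibrutinib maintenance treatment". Aim 1c, "Determine concentrations of Th1 and Th2 cytokines in plasma", sits under an aim that compares values from before and after ibrutinib is started. Aim 2 is to "Characterize the B- and T-cell repertoire during and after ibrutinib maintenance using immune receptor high-throughput sequencing".

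**Assays (Section 8, Table 3).** The columns are pre-HCT, pre-ibrutinib, 6, 12 and 18 months. The row "Cytokine Analysis and BAFF (plasma 1") is marked for all subjects at pre-HCT, 12 and 18 months and has dashes at pre-ibrutinib and 6 months. The CyTOF, T-cell repertoire and IgG/IgM rows are marked for all subjects at every column, including pre-ibrutinib.

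**Samples.** Section 8 collects blood before conditioning, "before ibrutinib initiation; and then again at Day +180, 1 year, and 1.5 years after allogeneic HCT", and stores three plasma vials of 1.5 mL from each 50 mL recipient draw at -80° C. Section 4 also takes research blood within two weeks of starting ibrutinib, and later for mixed lymphocyte reactions, Th1/Th2 assays "and other correlative science at Day +90; Day +180; 1 year; 1.5 years; and 2 years post-transplant". The Section 9 calendar agrees with Section 4, including the 2-year draw.

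**Treatment period.** The synopsis has ibrutinib "starting between Day +60 and Day +90 after allogeneic HCT and continuing until 18 months post-transplant", and Section 4.2 also gives 18 months post-transplant. Section 5.1 gives a duration of one year.

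**The concern.** This is a single-arm study (Section 2.4), so evidence on what ibrutinib does to plasma cytokines and BAFF comes mainly from change within subjects. That needs a value taken after the transplant and shortly before the first dose. Table 3 leaves out that value for this one assay. Conditioning, replacement of the recipient's immune system by the donor's, and immunosuppression all fall between the pre-HCT sample and ibrutinib. Section 2.2 itself links raised BAFF to chronic GvHD, which is a consequence of the transplant. A shift from pre-HCT to 12 months therefore could not be assigned to the drug. The one planned comparison with patients transplanted without ibrutinib (aim 2a) is listed under repertoire sequencing, not under cytokines or BAFF.

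The second question is whether the schedule contains a value from after treatment, which aims 2 and 3d both ask for. That depends on when treatment ends, and the protocol gives two answers.

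**Working it through.** The plan states no figure to reproduce here. The check sets the schedule against the aims and then does the day arithmetic.

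**1. The row against the aims**

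| Aim needs | Assayed in Table 3 | Comment |
|---|---|---|
| Before ibrutinib | pre-HCT only | dashes at pre-ibrutinib |
| During | 12 months | dashes at 6 months |
| After | 18 months at the latest | depends on the treatment duration |

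All five cells of this row are filled in, so the dashes are entries and not gaps from text extraction. Blank cells in the B-cell repertoire, T-follicular and H-Y rows may be merged cells, and nothing is inferred from them.

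**2. Distance of each baseline from the first dose**

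Ibrutinib starts between Day +60 and Day +90.
- Pre-HCT sample: at least 60 to 90 days earlier, plus the conditioning period.
- Pre-ibrutinib sample: at most 14 days earlier (Section 4).

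The pre-HCT value reflects the recipient's own immune system. The pre-ibrutinib value reflects the reconstituting donor system on which the drug will act.

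**3. Is the 18-month sample off drug?**

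Inputs: 1 month = 365.25/12 = 30.44 days, so 12 months = day 365, 18 months = day 548 and 2 years = day 730.5. The window is ±28 days at 18 months (Sections 4 and 9) and at 2 years (Section 4).

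*Treatment to 18 months (synopsis, Section 4.2).*
- 18-month draw: 548 − 548 = 0 days after the planned last dose; with the window, 28 days before to 28 days after. It is an end-of-treatment value.
- 2-year draw: 730.5 − 547.9 = 182.6 days after the planned last dose; with the window, about 155 to 211 days.

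*Treatment for one year (Section 5.1), assumed to count from the first dose.*
- Stop day: 60 + 365.25 = 425 to 90 + 365.25 = 455.
- 18-month draw: 548 − 455 = 93 to 548 − 425 = 123 days off drug; with the window, 65 to 151 days.
- 12-month draw: 60 to 90 days before the stop, so on drug.

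| Duration | 12 months | 18 months | Scheduled off-drug column in Table 3 |
|---|---|---|---|
| To 18 months | on drug | end of treatment | none |
| One year from first dose | on drug | about 93 to 123 days off drug | 18 months |

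With an 18-month stop, the missing off-drug column affects every row of Table 3, including the repertoire row that serves aim 2. The missing pre-ibrutinib value affects only the cytokine/BAFF row and is the same under either duration.

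**4. Is the material available?**

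Pre-ibrutinib: yes. Section 8 draws the blood and banks the plasma, and Table 3 gives the first plasma vial no other listed use at that visit. At 2 years: blood is drawn under Sections 4 and 9, but the Section 8 processing and storage text stops at 1.5 years, so banked 2-year plasma cannot be assumed.

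**The case against.** **A pre-HCT value is literally before ibrutinib, and the dashes look deliberate.** Both are true, so it would go too far to infer that the schedule cannot address its aim at all. A pre-ibrutinib baseline would not isolate the drug either, because reconstitution continues and immunosuppressants are tapered after Day +60. It would, however, remove conditioning and engraftment from the comparison. The plan uses that baseline in three other rows and gives no reason for leaving it out here.

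**A reader might infer that no subject will have a post-ibrutinib value.** The documents do not establish this. Under Section 5.1 the 18-month sample is off drug. Even with an 18-month stop, subjects who discontinue early, or whose 18-month visit falls late in its window, could give off-drug values. Those would be incidental, and early stoppers are a selected group.

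**A reader might infer that the Day +90 and 2-year blood has no planned use and could be dropped.** Section 4 contradicts that: it names mixed lymphocyte reactions and Th1/Th2 assays for those draws. The fault is only that Section 8 and Table 3 do not list them.

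**The secondary objective does not name BAFF or plasma cytokines.** Correct. It names Th1/Th2 polarization, T follicular cells, repertoire, immunoglobulins and alloantibody. The link for this row runs through aims 1c and 3d.

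**Little is lost, because frozen plasma can be assayed later.** This stands for the pre-ibrutinib sample and is why the point is minor. It does not extend to 2 years, where no plasma storage is described.

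**Conclusion.** The point holds as a minor one. Table 3 schedules no pre-ibrutinib cytokine/BAFF assay, so the only earlier value precedes conditioning, and a change from it cannot separate transplant from ibrutinib. This does not depend on the treatment duration.

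The absence of a scheduled off-drug time point is conditional. It holds if treatment runs to 18 months (synopsis, Section 4.2) and does not hold under the one year in Section 5.1, read as one year from the first dose. The documents do not settle which applies.

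It would be tempting to count the loss as every enrolled subject, or to say that every subject could have both values. Neither follows. Section 12.1 assumes that 45 of 50 reach ibrutinib, some of those will die or leave follow-up before 2 years, and 2-year plasma banking is not described.

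The effect is confined to an exploratory correlative aim. The primary endpoint, sample size, power and safety monitoring are untouched.

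**What to change.** 1. In Table 3, mark the cytokine/BAFF row at pre-ibrutinib, in addition to or in place of pre-HCT, using the plasma already stored under Section 8. Cost: at most about 45 to 50 extra assays, or none if the pre-HCT assay is moved, and no new draw. Moving it gives up the pre-transplant value.
2. Reconcile the ibrutinib duration in Section 5.1 with the synopsis and Section 4.2.
3. If 18 months stands, add the 2-year draw already in Sections 4 and 9 to the Section 8 collection and plasma-banking text, and add a 2-year column to Table 3, for subjects still in follow-up. Cost: processing and storage at that visit and up to one further assay per subject for each row extended, with no added blood draw.
4. Make the Section 8 draw times agree with Sections 4 and 9, including Day +90, and state there which assays each draw serves. Keep the Day +90 and 2-year draws. This is an edit to the text only.
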